Music may have a positive impact on pain and distress for children undergoing intravenous placement. Benefits were also observed for the parents and health care providers.

This study uses similar methods and looked for similar outcomes as Music:Ed, but using recorded rather than live music, and in a non-emergency setting.

The Music:ED study will therefore use a controlled experimental design to investigate the impact of using therapeutic live music in the Alder Hey Paediatric Emergency Department to reduce pain and distress during interventional procedures.

The outcomes of the study will provide evidence for the use of live music in the PED to support and enhance patient experience. Distress is often particularly high within the emergency department. If a patient's experience whilst attending the Emergency Department can be less traumatic, this will be of benefit to all: patients, families and clinicians. A patient who is less distressed is more cooperative and may be easier and quicker to treat.

Methodology and Methods

Research Question

Does live music decrease the pain and distress of patients undergoing a procedure within the paediatric emergency department?

Aims of the Study

Our aims/objectives include:

1. To explore whether live music helps to decrease pain and distress in patients in the Paediatric Emergency Department
2. To explore whether procedures can be carried out with greater ease from a clinician's perspective and whether staff experience of the situation is impacted by the presence of live music.
3. Exploring the overall impact on the ED experience from the patients, families and clinicians' perspectives.

Methodological Approach

We have chosen a mixed method design to provide us with different forms of data and insights from multiple practitioner, parent and patient perspectives throughout the experience.

Quantitative data includes collecting information about the patient's pain levels and qualitative data will be collected from open response questionnaires to explore patient distress and the practitioner, parent and patient perspectives on the experience.

Methods

There will be an experimental (live music) and a control (no live music) group.

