Research Nurses will identify appropriate patients using a screening tool that will outline the inclusion/exclusion criteria. Participant Information Sheets (PIS) will be provided to patients and their families for their appropriate ages. They will be offered a copy of the results if they would like and will be told how the results will be reported when the study is completed.

After gaining written consent from the parent and written or verbal assent from the child, Wong-Baker pain scoring methods will be explained in advance of the procedure. Necessary data will be collected for the CRF.

The participant's involvement in the study will be limited to the length of time of their Emergency Department visit, so will be just one day and one procedure.

For the experimental (music) group, Cascade's musicians will spend eight weeks, twelve hours per week in the ED and will aim to recruit all eligible children during that period. As this is a pilot study recruitment targets need to remain flexible, but are estimated at 60-80 participants (per group).

The same number of participants will be recruited to the control (no live music) group as a comparison, on days that the musicians are not in the department. All patients in both groups will continue to receive standard care. Each child can only be in the study once and for one procedure. Patients will be free to withdraw from the study at any time.

Following the procedure and interviews, patients involved will be offered a sticker and a CD of calming music recorded by Cascade Music as a thank you for their participation. For ethical reasons, this will not be mentioned in advance.

Timeline:

December 2018:

Implementation of study including finalising ethical approval

Recruitment of Research Nurse,

Publicise study within Alder Hey Children's Hospital's Emergency Department.

January - March 2019:

Recruitment of participants to the study, both experimental (music) and control (non-music) groups.

Data collection from participants.

March - May 2019:

Complete data analysis

Write report

Explore dissemination options including publishing and conferences

Plan next funding application

Methods of data collection and analysis

Three sets of data will be collected:

1. Quantitative: Self-reported pain.

A validated observational tool will be used: Wong Baker Faces.

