This is suitable for children age 3+. As children self-report, the Research Nurse will collect this data on a paper CRF. Wong Baker scores will be collected before, during and after the procedure. If mid-procedure collection of pain score is inappropriate, then participants can be asked about mid-procedure pain scores after the procedure.

A self-reported pain score will also be taken in advance, during the recruitment process, to provide a baseline measure.

2. Quantitative: Observed pain.

Data will be collected on observed pain levels using a validated observational tool: Faces, Legs, Activity, Cry and Consolability (FLACC) pain assessment tool.

This tool is suitable and validated for all ages of the recruited participants, from 6 months until 16 years. References regarding justification of this scale for these age ranges are below.^{5 6}

Scoring will take place before, during and after the procedure.

The Research Nurse will carry out this scoring, and when available, an independent observer from the Emergency Department staff will also. The Research Nurse will collect this data on the paper CRF.

Heart rate will also be monitored throughout, where a child is cooperative enough. HR will be noted approximately every two minutes before, during and after procedure, (cleaning marks the beginning of the procedure, final bandage/dressing marks the completion). The Research Nurse will note HR data on the CRF. There will be an option for the Research Nurse to record 'not available' for heart rate measurements either because child refuses or because of probe or monitor issues etc.

3. Qualitative: Distress and experiences of patients, families and clinicians.

Our outcome measures will include collecting qualitative information on patient's distress, and patients', families' and clinician's Emergency Department experience. All recruited patients will receive a paper questionnaire with open text response options.

Qualitative questions for Experimental AND Control Groups:

The following two questions will be asked of both the experimental (live music) AND control (no live music) groups. The questions will be asked of each of these two people: patient and parent/legal guardian.

'Please answer the following questions, in particular, in regard to distress levels/lack of distress':

- Qualitative question 1. What do you think helped you/your child during their procedure?

- Qualitative question 2. Did anything make the situation worse?

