Qualitative questions for Experimental Group Only:

Within the experimental group only, the following three additional questions will be asked, via a paper questionnaire, of each of these three people: patient, parent/legal guardian and clinician. These questions directly link to the objectives of the study.

These questions are in particular regard to music, which is why they would not be appropriate to be asked of the control (no live music) group.

- Qualitative Question 1. How did you feel the music affected the child's distress before, during and after the procedure?

- Qualitative Question 2. Can you tell me about how the live music helped or hindered the procedure?

- Qualitative Question 3. Can you tell me about your experience of the ED (Emergency Department) today, in particular in regard to the music?

The qualitative questions will be included in a open ended questionnaire style sheet which the parent, child or practitioner if the parent wishes, can fill out between the end of the music intervention and when they are discharged from the ward. It will be collected by the RN and stored in a secure room in a locked filing cabinet.

Target population and sampling

This will be a single centre study.

Study participants for both the control and experimental groups of the study will be recruited from AHCH Emergency Department. The study population will consist of children between the age of 6 months and 16 years needing to undergo a painful procedure from a specified list. The Research Nurse will use a screening tool to assess eligibility within this age group.

Necessary data will be collected for the CRF by the Research Nurse:

CRF:

Patient's name

Patient's age

Patient's gender

Parent(s)/legal guardian in attendance during procedure (names)

Whether or not the patient has had this procedure before

How many times the child has visited the hospital in the last 12 months

Have they had an upsetting hospital experience in the past? Yes or no

Record a Wong-Baker pain score at this point (for children age 3+) as a baseline measure

Record whether patient has had analgesia in advance, or during hospital visit

Record use of local anaesthetics e.g EMLA/amecop, LAT gel, cold spray (ethyl chloride)

Record use of Entonox during the procedure

Record if other distraction methods were also used

(Play Specialist/books/bubbles/IPad/TV/ iPhone/ staff dancing and singing, etc)

Record whether the procedure was successful

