Quantitative data will be entered into SPSS. We will analyse the data using the chi-square test for trend, paired samples t-tests and Wilcoxon sign ranks tests as appropriate. Participants with missing data (either before procedure or after procedure) will be excluded from analysis. NVivo 10 Software will be used to assist in the organization and coding of qualitative data (e.g. free text open question responses). Qualitative thematic analysis will be interpretive and iterative. Our approach to synthesizing qualitative and quantitative data will draw on the constant comparative method.

Dissemination

Findings from the study will be disseminated to professionals and to children and their families. Dissemination potentially includes publication in journals and via presentation at conferences and at practice development workshops. This will be done locally through the associated universities and hospitals as well as potentially internationally. By working with colleagues in clinical practice on an on-going basis throughout the study, the researchers anticipate that the study will have a direct impact on practice.

Benefit to patients

Findings will be used to further our understanding of the potential benefits of using live music within the Paediatric Emergency Department, with an aim to improve patient experience.

Link to Alder Hey Research & Universities' Strategies

Alder Hey Children's Hospital's strategy is to build a healthier future for children and young people. One of Alder Hey's main aims is to 'ensure all of our patients and their families have a positive experience whilst in our care'. This study very much follows this ethos, by exploring ways to make the hospital experience a less traumatic one.

A key strength of the University of Liverpool's research strategy is its impact intensive approach. The design of this study will explore ways of making immediate, effective improvements to the care of children and young people.

References:

¹ A. Y. R. Kühlmann(2018) *Meta - analysis evaluating music interventions for anxiety and pain in surgery*. Available at 002 <https://onlinelibrary.wiley.com/doi/abs/10.1/bjs.10853>

² Kari Sand-Jecklin, EdD, MSN, RN, AHN-BC, Howard Emerson, BA, CMP (2010) *The Impact of a Live Therapeutic Music Intervention on Patients' Experience of Pain, Anxiety, and Muscle Tension* *Holist Nurs Pract* 2010;24(1):7–15

³ *J Dev Behav Pediatr.* 2007 Oct;28(5):399-403.

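### The recruitment Wong-Baker score is collected as a baseline, but none of the named tests adjusts the music-control pain comparison for it

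*Protocol*

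**What the plan says.** The Protocol, under Methods, sets up two groups: "There will be an experimental (live music) and a control (no live music) group". They are not randomised. On controls it says "The same number of participants will be recruited to the control (no live music) group as a comparison, on days that the musicians are not" present. On size it says "As this is a pilot study recruitment targets need to remain flexible, but are estimated at 60-80 participants (per group").

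Under self-reported pain, in the section on data collection and analysis, it says "Wong Baker scores will be collected before, during and after the procedure". It then adds a further, separate measurement: "A self-reported pain score will also be taken in advance, during the recruitment process, to provide a baseline measure". The CRF list under Target population and sampling repeats this: "Record a Wong-Baker pain score at this point (for children age 3+) as a baseline measure".

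Data Analysis names the quantitative tests in one sentence: "We will analyse the data using the chi-square test for trend, paired samples t-tests and Wilcoxon sign ranks tests as appropriate". The missing-data rule follows: "Participants with missing data (either before procedure or after procedure) will be excluded from analysis". That rule does not mention the recruitment score. No regression, ANCOVA or other adjusted model appears anywhere in the Protocol.

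**The concern.** The research question is whether live music lowers pain, which is a comparison of music with control. The study asks children for a baseline score, but the stated analysis has no step in which that score informs the comparison.

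Two things are at stake. First, allocation follows the days on which musicians attend, so children in the two groups may arrive with different levels of pain. A comparison that ignores baseline carries part of that difference into the apparent music effect. Second, if presenting pain predicts procedural pain, ignoring it leaves the interval for the group difference wider than it need be.

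**Working it through.** **What each named test can do.**

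- Paired t and Wilcoxon signed-rank: both compare two time points within the same children. No matching of music to control children is described, so neither test gives a group contrast.
- Chi-square for trend: applied to group by ordered pain score, it can contrast the groups. Its statistic is essentially (N − 1)r², with r the correlation between group and score. It is therefore an unadjusted comparison of mean scores, with no place for a covariate.

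**Inputs.** From the Protocol: 60 to 80 per group, roughly 1:1. The Protocol gives no alpha, power, effect size, SD or correlation, so there is no figure to reproduce. Assumed: two-sided alpha 0.05, 80% power for the detectable difference, equal SDs at baseline and outcome, and rho from 0.1 to 0.7.

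**Precision.** The variance of the group difference, relative to the unadjusted comparison, is 1 − rho² for ANCOVA. The detectable difference in SD units is (1.960 + 0.842) × √(2/n) × √(1 − rho²). Unadjusted, this is 2.802 × √(2/60) = 0.511 at 60 per group and 2.802 × √(2/80) = 0.443 at 80.

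| rho | Relative variance | Saving | Detectable, n = 60 | Detectable, n = 80 | Power for 0.5 SD, n = 60 |
|---|---|---|---|---|---|
| unadjusted | 1.00 | – | 0.511 | 0.443 | 78.2% |
| 0.1 | 0.99 | 1% | 0.509 | 0.441 | 78.6% |
| 0.2 | 0.96 | 4% | 0.501 | 0.434 | 79.8% |
| 0.3 | 0.91 | 9% | 0.488 | 0.423 | 81.9% |
| 0.5 | 0.75 | 25% | 0.443 | 0.384 | 88.5% |
| 0.7 | 0.51 | 49% | 0.365 | 0.316 | 97.0% |

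At rho 0.5 the interval is 1 − √0.75 = 13% narrower; at rho 0.1 it is 1 − √0.99 = 0.5% narrower.

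Only children aged 3 and over self-report, and the Protocol does not say what share they will be. If it were 80% of 60, that is 48 per group, and the detectable difference is 0.572 SD unadjusted and 0.495 SD adjusted at rho 0.5.

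**Imbalance.** If mean baseline pain differs by Δ SD between groups, an unadjusted comparison of later scores estimates the effect plus rho × Δ. With rho 0.5 and Δ = 0.3 SD, the residue is 0.15 SD.

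A simulation used 70 per group, 4,000 runs, rho 0.5, no music effect and a 0.5 SD fall common to both groups. Percentages are runs with p < 0.05:

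| Test | No imbalance | 0.3 SD imbalance |
|---|---|---|
| Trend test on later score | 5.1% | 13.7% |
| ANCOVA | 4.8% | 4.6% |

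With no imbalance, the paired t-test within the music group was significant in 98% of runs although music did nothing. It cannot stand in for the group comparison. The simulation uses continuous normal scores, and imbalance enters only through the measured baseline, so ANCOVA is the correct model by construction. Clustering by day is not modelled.

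**The case against.** **This belongs in an SAP.** Choice of covariates is often left to an SAP, and one may exist. That would be decisive if the Protocol deferred, but it does not: it commits to three named tests, and its closing qualifier chooses among those three. A reader might infer that the recruitment score will not be used at all. The text does not say that, since the score could describe the groups. What stands is that no named test adjusts for it.

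**The gain may be negligible.** Presenting pain and pain from, say, cannulation may be weakly related, and analgesia, topical anaesthetic, Entonox and distraction may intervene. At a true difference of 0.4 SD and 60 per group, power moves only from 58.4% to 58.9% at rho 0.1 and 60.2% at rho 0.2. This stands, and it is why no single gain should be quoted.

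**A stronger reading.** A reader might infer that the plan compares before-to-after changes between groups, and criticise it for the variance factor 2(1 − rho), which exceeds 1 when rho is below 0.5. The Protocol names no between-group change-score test and no two-sample t-test, so power figures for such tests are not figures for this plan.

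**Precision is the wrong frame without randomisation.** Raw and adjusted contrasts then need not target the same quantity. This largely stands. It moves the weight of the argument from precision to imbalance in presenting pain.

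**It is a pilot.** Numbers are flexible and no power target is set. That limits the urgency. The effect question is still stated, and a further funding application is planned.

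**Conclusion.** The point holds in a limited form. A baseline is collected by design, and no named test uses it to adjust the music-control comparison of self-reported pain. The consequence is a residue of about rho times any imbalance in presenting pain, together with some lost precision.

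Neither size is fixed by the Protocol. The variance saving is 1% at rho 0.1 and 25% at rho 0.5, and the bias depends on an unknown imbalance. The figures assume equal SDs and a linear relation, and apply only to Wong-Baker in children aged 3 and over. FLACC, used at all ages, is unaffected.

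Two further inferences are not supported. The whole of a baseline difference does not pass into an unadjusted comparison, only about rho times it. Nor would adjustment make the groups comparable: other differences between musician and non-musician days would remain.

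**What to change.** In Data Analysis:

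1. Name the recruitment Wong-Baker score as the baseline, distinct from the score taken just before the procedure. The music-group questionnaire asks about the music's effect before the procedure as well, so the later score may already reflect it.
2. State that the during- and after-procedure Wong-Baker scores in children aged 3 and over will be compared between music and control by a linear model (ANCOVA) with group and the recruitment score. Report the adjusted mean difference with its 95% CI, with an ordinal model on the same terms as a check.
3. Keep the paired tests as within-group description only.
4. Handle a missing recruitment score by multiple imputation, or by complete cases with a sensitivity analysis. Filling in the mean with a missing indicator is justified mainly under randomisation and is not well suited here.
5. State that this adjustment does not remove other confounding by day.

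The cost is a few sentences and routine additional analysis, with no new data, visits or patients. The downside is one degree of freedom and a linearity assumption, with little gain if the correlation proves low.
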